5.4.2. Histopathology Report Terminology

Any histopathological lesions will be biopsied or excised locally according to local medical practice. Histopathological reports on biopsy and excision specimens will be performed locally and **written** according to local medical practice. ~~All histopathological reports will be recorded in the eCRF.~~

~~The following categories could be classified:~~

- ~~• Negative.~~
- ~~• Low grade squamous intraepithelial lesion (condyloma / cervical intraepithelial neoplasia grade 1 (CIN1) / vaginal intraepithelial neoplasia grade 1 (VAIN 1) / vulval intraepithelial neoplasia grade 1 (VIN 1)).~~
- ~~• High grade squamous intraepithelial lesion (cervical intraepithelial neoplasia grade 2 (CIN2) / vaginal intraepithelial neoplasia grade 2 (VAIN 2) / vulval intraepithelial neoplasia grade 2 (VIN 2)).~~

- ~~High grade squamous intraepithelial lesion (cervical intraepithelial neoplasia grade 3 (CIN3) / vaginal intraepithelial neoplasia grade 3 (VAIN 3) / vulval intraepithelial neoplasia grade 3 (VIN 3)).~~
 - ~~Adenocarcinoma *in situ* (AIS).~~
- ~~Invasive malignancy.~~

5.4.5. Abnormal cytology

Observation of ≥ LSIL (low grade squamous intraepithelial lesion) will result in referral to colposcopic evaluation, ~~irrespective of the oncogenic HPV DNA test result.~~

5.5. Colposcopic evaluation

Colposcopy will be performed according to local medical practice ~~on women with abnormal cytological findings.~~ All colposcopies will be recorded in the eCRF and every attempt will be made to document colposcopy performed outside the study in the specific section on the eCRF.

Any cervical lesions will be biopsied or excised according to local medical practice. In addition, the vagina and vulva may be inspected with each colposcopy ~~and any vaginal or vulval lesions possibly associated with HPV (other than condylomas) may be biopsied or excised according to local medical practice.~~ All tissue will be processed locally.

5.6. Management of cervical lesions

Any further management following local cervical therapy for cervical lesions will be handled according to local medical practice within the local health care system. The treatment of cervical, ~~vaginal or vulval~~ lesions (***or other lesions detected during the medical evaluation such as vaginal or vulval lesions***) ~~possibly associated with HPV~~ is to be handled according to local medical practice.

5.7. Outline of study procedures

Table 1 List of study procedures

Visit	VISIT 1	VISIT 2	VISIT 3	VISIT 4
Timing (Months post concluding HPV-015 visit (Visit 9, or Visit 11 or last HPV-015 study visit as planned in the HPV-015 protocol amendment 4))	Month 12	Month 24	Month 36	Month 48
Review and record oncogenic HPV infection status, if applicable	○**	○**	○**	○**
Review and record cervical cytology status	○**	○**	○**	○**
Record concomitant medication/ vaccination , if applicable	●	●	●	●

** Amended 21 June 2010

5.8.2.4. Cervical sampling

- Collect sample for cervical liquid-based cytology examination (ThinPrep® PapTest) and ~~oncogenic HPV DNA (HC2HCII) testing will be performed, if applicable.~~

5.8.2.5. Review ~~and record~~ oncogenic HPV infection status and cervical cytology status

- Review ~~and record~~ oncogenic HPV infection status, *if applicable*.
- Review ~~and record~~ cervical cytology status.

5.8.2.6. Recording of referral to colposcopy and treatment (if applicable)**5.9.1. Use of specified study materials**

When materials are provided by GSK Biologicals *or Quest Diagnostics*, it is MANDATORY that all clinical samples be collected and stored exclusively using those materials in the appropriate manner. The investigator must ensure that his/her personnel and the laboratory(ies) under his/her supervision comply with this requirement. However, when GSK Biologicals *or Quest Diagnostics* does not provide material for collecting and storing clinical samples, then appropriate materials from the investigator's site are to be used. Refer to the module of clinical trial supplies in the SPM.

5.9.4.1. Cytology

Cervical cytology will be performed using the ThinPrep® PapTest (Cytoc Corporation, Boxborough, MA, USA), by Quest Diagnostics (Teterboro, NJ, US), or another GSK designated laboratory. Cervical cells for ThinPrep® cytology ~~at scheduled 12-month interval visits~~ will be collected using the sampling device provided *and* rinsed into a collection vial containing PreservCyt® medium (provided by ~~sponsor~~ *GSK Biologicals or Quest Diagnostics*).

(Note, also amended in Appendix A)

5.9.4.2. HPV DNA Testing by Hybrid Capture 2II (HC2HCII)

After ThinPrep® cytology slides have been prepared, residual PreservCyt® specimens on slides ~~for all samples~~ *read as normal or ASCUS* will be tested for HPV DNA. Testing will be done by Quest Diagnostics (Teterboro, NJ, US), or another GSK designated laboratory using the Hybrid Capture® 2II test (HC2HCII; Digene Corp., Gaithersburg, MD, USA). Probe B will be used and is designed to detect infections with one of 13 oncogenic HPV types (HPV types 16, 18, 31, 33, 35, 39, 45, 51, 52, 56, 58, 59 and 68) [Vernick 2003, Digene Corporation 2002]. This test does not provide type-specific data.

(Note, also amended in Appendix A)

8.6. Unblinding

For subjects who conclude the HPV-015 study at Visit 9 or Visit 11, but agree to remain blinded until the final analysis *of study HPV-015*, the following applies:

8.7. Emergency unblinding

For subjects who conclude the HPV-015 study at Visit 9 or Visit 11, but agree to remain blinded until the final analysis *of study HPV-015*, the following applies:

GSK Biologicals Central Safety Physician (Study Contact for Emergency Code Break)	
Mobile phones for 7/7 day availability:	
Outside US/Canada: PPD [redacted]	(GSK Biologicals Central Safety Physician on-call)
For US/Canada only: PPD [redacted]	(Head Safety Evaluation and Risk Management North America GSK Biologicals Central Safety Physician on-call)
Back-up mobile phone contact: PPD [redacted]	
Outside US/Canada: PPD [redacted]	
For US/Canada only: PPD [redacted]	

GlaxoSmithKline Biologicals Clinical Research & Development Protocol Administrative Change 1	
eTrack study number and Abbreviated Title(s)	113617 (HPV-062 EXT:015)
IND number	BB-IND 7920
EudraCT number	2009-017282-35
Administrative change number:	Administrative change 1
Administrative change date:	Administrative change 1 Final: 18 August 2010
Co-ordinating author:	PPD Scientific Writer
Rationale/background for changes: Since the double-blind study HPV-015 will be extended by a maximum of three additional years, according to Protocol Amendment 4, dated 24 March 2010, it is important that central study staff involved in the studies remains blinded till the end of study HPV-015 for all subjects who have been participating in HPV-015 and will be participating in this study. Therefore, subjects enrolled in HPV-015 extension studies such as study HPV-062 cannot retain the HPV-015 subject number as is stated in the original protocol. Consequently, different identification numbers will be provided by an external statistician.	

Amended text has been indicated in *bold italics* and deleted text has been indicated in ~~strikethrough~~ in the following sections:

Section 5.2.1. Subject identification

~~Subjects will retain their identification numbers from study HPV-015.~~

A new identification number will be assigned to the subject to preserve the blind for HPV-015 data during this HPV-015 extension study.

CONFIDENTIAL

113617 (HPV-062 EXT:015)
Final

Protocol Sponsor Signatory Approval

eTrack study number and Abbreviated Title	113617 (HPV-062 EXT:015)
IND number	BB-IND 7920
EudraCT number	2009-017282-35
Date of protocol	Final: 03 March 2010
Detailed Title	A phase IIIb, open, multi-centre gynaecological extension study for the follow-up of a subset of HPV-015 study subjects

1. DOCUMENT HISTORY

Date	Description	Protocol Version
22-OCT-2014	Version 1	Administrative Change 1 Final: 18 August 2010

2. STUDY DESIGN

Figure 1 Study visits and study procedures

*Subjects with two positive oncogenic HPV DNA tests or one cervical cytology reading \geq ASC-US (atypical squamous cells of undetermined significance) positive for oncogenic HPV DNA or one cervical cytology reading \geq LSIL (low grade squamous intraepithelial lesion) will be referred for colposcopy evaluation according to the clinical management algorithm. Oncogenic HPV tests (HCII) will only be performed on normal and ASCUS cytological samples.

** Study conclusion, see dotted line (-), will occur after any given visit that required treatment of cytological abnormality, any given visit with a negative oncogenic HPV DNA test and normal cervical cytology or the closing of study activities related to Visit 4.

[figure not shown]
- **Experimental design:** A phase IIIb, open, multi-centre study with one group.
- **Treatment allocation:** None.
- **Blinding:** Open.
- **HPV-015 concluding visit:** Subjects who participated in the HPV-015 study may decide to conclude their participation in the HPV-015 study at Visit 9, Visit 11 or at the last study visit in HPV-015 planned under protocol amendment 4.

Statistical Analysis Plan	
Study alias & e-track number(s): HPV-062 EXT:015 (113617)	

- **Treatment groups:** One study group consisting of a subset of HPV-015 subjects who at their concluding HPV-015 study visit:
 - displayed normal cervical cytology but tested positive for oncogenic HPV infection
 - were pregnant so that no cervical sample could be collected at that visit

The study eligibility algorithm is presented in [Figure 2](#).

Figure 2 HPV-062 EXT:015 study eligibility algorithm

- **Vaccination schedule(s):** None.
- **Control:** None.
- **Type of study:** Gynaecological follow-up extension study of a subset of HPV-015 study subjects.
- **Data collection:** Remote Data Entry (RDE).
- **Duration of the study:** Maximum of four years for each subject.
- **Study visits per subject:** Up to four scheduled visits at approximately Months 12, 24, 36 and 48 after each subject’s concluding HPV-015 study visit.

Subjects are eligible to join the study at any visit.

• **Study procedures:**

Subjects will enter the study approximately one year after their HPV-015 concluding visit. Annual visits will be scheduled for a maximum study duration of approximately four years.

Statistical Analysis Plan	
Study alias & e-track number(s): HPV-062 EXT:015 (113617)	

At each visit, a gynaecological examination will be performed and cervical liquid-based cytology samples will be collected for cervical cytology examination and oncogenic HPV DNA testing, if the cytology reading is normal or ASCUS.

The presence of oncogenic HPV infection will be determined by the Hybrid Capture® II (HCII) test, which detects HPV DNA types 16, 18, 31, 33, 35, 39, 45, 51, 52, 56, 58, 59 and 68 [Vernick, 2003, Digene Corporation 2002]. Cervical cytology examination will be performed using the ThinPrep®Pap test.

Continued study participation as well as further referral/treatment will be based on the test results from each visit, and will be aligned with the clinical management algorithm which is aligned with the 2009 American Society for Colposcopy and Cervical Pathology (ASCCP) guidelines for use of HPV DNA testing as an adjunct to cytology for cervical cancer screening in women 30 years or older.

The following clinical management algorithm will be applied, refer to [Figure 3](#).

- Subjects with normal cervical cytology and who are oncogenic HPV DNA negative, will end their participation in the study.
- Subjects with normal cervical cytology, but who are oncogenic HPV DNA positive in one single test, will be asked to return at the next study visit.
This outcome will only be applicable to subjects who were pregnant at their concluding HPV-015 study visit so that no cervical sample could be collected at that visit.
- Subjects with normal cervical cytology, but who are oncogenic HPV DNA positive in two subsequent tests, will be referred to colposcopy. The result of the subjects' last HPV-015 study visit will be taken into account at Visit 1.
- Subjects with a single cervical cytology reading of \geq ASC-US (atypical squamous cells of undetermined significance) and positive for oncogenic HPV DNA will be referred to colposcopy.
- Subjects with a single cervical cytology reading of \geq LSIL (low grade squamous intraepithelial lesion) will be referred to colposcopy.

Please note that a missing result for HCII will be managed as oncogenic HPV positive.

In case of referral for colposcopy, the post-colposcopy follow-up strategies are:

- If no lesion is detected or the detected lesion does not require any treatment, subjects will be asked to return at the next study visit.
- If a lesion that requires treatment is detected, the subject should be referred to treatment according to local medical practice. Any further management following local cervical therapy for cervical lesions will be handled according to

Statistical Analysis Plan	
Study alias & e-track number(s): HPV-062 EXT:015 (113617)	

[figure not shown]
local medical practice within the local health care system. After treatment, the subject's participation in the study will end.

As management algorithms cannot define every clinical situation, it is the investigator's (or his/her designee's) responsibility to exercise appropriate clinical judgement in the medical management of each individual case.

Once their study participation ends, all subjects should be referred to their local health care system.

Subjects who have not developed cervical lesions by the end of the study, but who are still positive for oncogenic HPV infection, should be informed of the potential risks of being positive for oncogenic HPV DNA, and the importance of continued follow-up.

Figure 3 Clinical management algorithm

HPV DNA test (HCII) = Hybrid Capture® II test detecting HPV types 16, 18, 31, 33, 35, 39, 45, 51, 52, 56, 58, 59 and 68. Specimens will be reported as "Quantity Not Sufficient" (QNS) in the case where there is an inadequate amount of cells for HCII and preferentially, a repeat sample will be collected. Missing HCII test results should be managed as oncogenic HPV positive
* = The result of the subject's concluding HPV-015 study visit will be taken into account. Subjects who were pregnant at that visit so that no cervical sample could be collected, and who display normal cytology but are positive for oncogenic HPV DNA at Visit 1, will return for the next study visit.

Statistical Analysis Plan	
Study alias & e-track number(s): HPV-062 EXT:015 (113617)	

** = Colposcopy and/or colposcopy-directed biopsies will be performed according to local medical practice.
 \$ = Oncogenic HPV tests (HCII) will only be performed on normal and ASCUS cytological samples.

- **Study visit activities and gynaecological follow-up reporting**
 - Gynaecological examination at Visit 1, Visit 2, Visit 3 and Visit 4.
 - Collection of cervical liquid-based cytology samples at Visit 1, Visit 2, Visit 3 and Visit 4 for cervical cytology examination and oncogenic HPV DNA testing, if the cytology reading is normal or ASCUS.
 - Referral to colposcopy according to protocol clinical management algorithm, if required.
 - Conduct of colposcopy, colposcopy directed biopsies and local cervical therapy according to local medical practice, if required.
 - Recording of colposcopic referral according to management algorithm, if required.
 - Recording of treatment referrals according to local medical practice, if required.
- **Safety reporting:**
 - All fatal SAEs will be reported.
 - All SAEs assessed as being possibly related to study participation will be reported.
 - All SAEs assessed as being possibly related to a concurrent GSK medication will be reported.
 - Withdrawal from the study due to adverse events (AEs) or SAEs will be reported.

No other AEs or SAEs for HPV-015 study subjects will be reported in this study. AEs and SAEs related to the vaccine administered in the HPV-015 trial should be reported as part of the HPV-015 study, as described in the HPV-015 study protocol.

The following group names will be used for the statistical analyses:

Group order in tables	Group label in tables	Group definition for footnote
1	HPV-062 study subjects	HPV-015 study subjects enrolled in HPV-062 who displayed normal cervical cytology but tested positive for oncogenic HPV infection at their concluding HPV-015 study visit. or who were pregnant at their concluding study visit were not able to provide a cervical sample

Statistical Analysis Plan	
Study alias & e-track number(s): HPV-062 EXT:015 (113617)	

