6. STATISTICAL METHODS

The analysis will be performed on the HPV-062 Total cohort

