6.1.1. Analysis of demographics

Demographic characteristics (age, race and gender), withdrawal status will be summarised using descriptive statistics:

Age: Age of a subject is computed by considering the date of birth and date of the first visit in this study for that subject. Age of a subject was computed as the time interval between two dates in specified time unit.

- Frequency tables will be generated for categorical variable such as race and gender.
- Mean, median, standard deviation will be provided for continuous data such as age.

The distribution of eligible subjects among the study sites will be tabulated.

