6.1.2. Descriptive analysis of clinical management

For each visit and overall:

- Results of oncogenic HPV DNA tests.
- Results of cervical cytology tests.
- Referrals to colposcopy, if required.
- Referrals to treatment according to local medical practice, if required.

Statistical Analysis Plan	
Study alias & e-track number(s): HPV-062 EXT:015 (113617)	

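### Should the SAP report HPV positivity and colposcopy referral separately for women who were HPV-positive and women who were pregnant at HPV-015 exit?

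*SAP*

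**What the plan says.** SAP section 2 describes "One study group consisting of a subset of HPV-015 subjects who at their concluding HPV-015 study visit" either had normal cytology with oncogenic HPV or were pregnant and could not be sampled. After the sentence "The following group names will be used for the statistical analyses", the table has a single row, and its footnote definition names both entry routes. Section 6 states that "The analysis will be performed on the HPV-062 Total cohort". Section 6.1.1 summarises age, race, gender and withdrawal status, and adds that "The distribution of eligible subjects among the study sites will be tabulated". Section 6.1.2 lists HPV DNA results, cytology results, colposcopy referrals and treatment referrals "For each visit and overall". Entry route appears in none of these displays.

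The management algorithm in SAP section 2 does use entry route. A single positive HPV test with normal cytology leads to a return visit, with the restriction "This outcome will only be applicable to subjects who were pregnant at their concluding HPV-015 study visit". The Figure 3 footnote says the same: women unsampled because of pregnancy who have normal cytology and "are positive for oncogenic HPV DNA at Visit 1, will return for the next study visit". For the other women, the HPV-015 exit result counts as the first of two positives, so the same finding leads to referral. The SAP also says: "Please note that a missing result for HCII will be managed as oncogenic HPV positive".

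The protocol matches. Section 3 has one group, section 10.3 one cohort, and section 10.6.4 asks for results per subject and overall, with no split by entry route.

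**The concern.** Oncogenic HPV positivity and colposcopy referral are two of the four endpoints, and at the first in-study sample the algorithm makes referral depend on how the woman entered. A pooled Visit 1 referral percentage therefore mixes women for whom one more positive test is enough with women for whom it is not. Pooled positivity likewise mixes persistence in women already known to be positive with prevalence in women whose status at exit was unknown. A reader might take the pooled percentage as the persistence rate of the first kind of woman. The SAP tabulates subjects by site, which the algorithm does not use, but not by entry route, which it does. What is at stake is interpretation: the report could not state, from its planned tables, how many women of each kind were managed or what happened to each kind.

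**Working it through.** **Where the routes differ.** They differ for one result only: normal cytology with HCII positive, or missing and so managed as positive, at the first sample. ASC-US with a positive HCII, LSIL or worse, and the normal/HCII-negative exit are handled alike in both routes. After the first sample the rules largely converge.

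**What pooling does.** Let w be the pregnant share, p the first-sample positivity in exit-positive women and q that in pregnant-route women. Take all cytology as normal.
- Pooled positivity = (1 − w)p + wq, which is w(p − q) below p.
- Pooled referral by the normal/HCII-positive route = (1 − w)p, which is wp below p.

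The documents give none of w, p or q. Protocol sections 4.1 and 10.2 give only about 1500 women expected to be eligible or invited, not split by route. Protocol section 1.1 gives a prevalence of 5% to 40%, but for any HPV in general populations and not for the 13 types the test detects. The values below are assumptions.

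| w | p | q | w(p − q), points | wp, points |
|---|---|---|---|---|
| 5% | 50% | 40% | 0.5 | 2.5 |
| 10% | 50% | 10% | 4.0 | 5.0 |
| 30% | 60% | 5% | 16.5 | 18.0 |
| any | 40% | 40% | 0 | w × 40 |

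The third row needs both extremes at once. The fourth shows that a positivity gap appears only if p exceeds q. The referral gap remains whenever w is above zero, because the rule itself differs.

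**Can the split be recovered from the planned tables?** Suppose a Visit 1 table of 1500 women shows 675 normal/HCII-positive and referred, 15 normal/HCII-positive and returned, and 810 HCII-negative (675 + 15 + 810 = 1500). The 810 could belong to either route, so several splits fit:

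| Pregnant-route women | Exit-positive positivity | Pregnant-route positivity |
|---|---|---|
| 75 | 675/1425 = 47.4% | 15/75 = 20.0% |
| 150 | 675/1350 = 50.0% | 15/150 = 10.0% |
| 450 | 675/1050 = 64.3% | 15/450 = 3.3% |

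The first and third rows fall outside assumed ranges of 50–60% for p and 5–40% for q. Inside those ranges:
- exit-positive women number between 675/0.60 = 1125 and 675/0.50 = 1350, so pregnant-route women number 150 to 375;
- 15/q with q of at least 5% allows at most 15/0.05 = 300 pregnant-route women;
- together this gives 150 to 300 women, p from 50.0% to 675/1200 = 56.3%, and q from 10% down to 15/300 = 5%.

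The answer is narrower but still not unique. Summary tables without a count by route do not fix the denominators.

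**Does the study need these rates?** SAP section 3 has one objective, to provide clinical management to both kinds of women together. SAP section 4 lists four occurrence endpoints, none specific to a route. Protocol section 10.2 calls the study descriptive, with no power evaluation, and section 1.2 says it is not intended for long-term efficacy, immunogenicity or safety data. A pooled count of positives or referrals among all women seen is exactly what these endpoints ask for.

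**Precision of a split.** If the pregnant route is small, its figures are loose. With Clopper–Pearson limits, the method in the SAP reference list, 15/150 is 10.0% (95% CI 5.7 to 16.0) and 5/50 is 10.0% (3.3 to 21.8).

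**The case for a change.** The strongest case for a change is that the split comes from the plan's own algorithm and is not an arbitrary subgroup. In a descriptive study the tables are the whole product, and one line giving the number of women by entry route would supply the missing denominator. The objective itself names both kinds of women. Because women may join at any visit, the by-visit tables do not isolate the first in-study sample either.

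Much of this stands. The planned tables do not give rates by route, and a count by route would help readers.

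It does not follow that the information is lost. Protocol Table 1 marks the inclusion check as documented in the eCRF, and protocol section 5.8.2.6 has the last HPV-015 result taken into account when referral is recorded, so sites need it. A later split may therefore be possible. That is not certain: the two routes form one either/or criterion in protocol section 4.2, subjects receive new identification numbers under section 5.2.1, and no section shows a route variable reaching the analysis dataset. The same uncertainty means the addition might cost more than a line. A display at the first in-study sample needs a derived time point that the SAP does not have, and an unstored route would require linkage back to HPV-015 while its blind is being preserved.

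**Conclusion.** The observation is correct, but it does not call for a change. The SAP follows the protocol in using one group and one cohort, the group footnote tells readers that both kinds of women are pooled, and the pooled results answer the stated endpoints without bias. What is missing is an additional description that no objective or endpoint requires.

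The size of any difference cannot be taken from the documents. On the assumed values above, pooled positivity lies 0 to 16.5 points, and first-sample referral by the normal/HCII-positive route 2.5 to 18.0 points, below the exit-positive women's rates. These are distances between the pooled rate and a rate the study does not set out to estimate. If entry route is already in the analysis dataset, analysts may reasonably show the number of women by route alongside the site distribution. The plan is sound without it. This conclusion would change only if the report presented the pooled percentages as persistence or referral rates in women known to be HPV-positive at exit, which the SAP does not propose.
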